#### **5.5 Interim Monitoring**

The analysis of study data to monitor for adverse or beneficial treatment effects will be the responsibility of the CSPCC. During the course of this study, reports will be prepared and distributed to the various groups that are responsible for the conduct of the study. These groups are the Executive Committee, the Data Monitoring Committee, the VA's Central IRB, and the Cooperative Studies Scientific Evaluation Committee (CSSEC). The Study Chairmen, the Executive Committee and the Cooperative Studies Scientific Evaluation Committee will not be privy to any of the results that compare the outcomes of the two treatment groups.

#### 5.5.1 Data Monitoring Committee

An independent oversight committee called the Data Monitoring Committee (DMC) will monitor study progress. This committee meets on the same basic schedule as the Study Group and Executive Committee, i.e., at 6 to 9 months after the start of participant recruitment and yearly thereafter. Initially, the DMC will meet to become acquainted with the study and to establish monitoring guidelines.

The main responsibility of the DMC members is to make a recommendation to the Director of the Cooperative Studies Program on whether the study should continue or not based on the reviews of the progress reports submitted to them. The study could be recommended for termination due to poor recruitment, treatment differences so large that it would be possible to reach a final decision about the main question of the study, treatment differences so small that continuation would be irresponsible, or due to safety concerns. The DMC also reviews the participating sites' performance in terms of recruitment, adherence to the protocol etc., and makes recommendations on them. Their final responsibility is to review all proposed protocol changes and suggested sub-protocols and to make recommendations in regards to their acceptability.

In order for the DMC to carry out its responsibilities, the CSPCC Study Team will provide the committee with a report approximately three weeks prior to their meetings. The report will consist of the tables describing number of participants enrolled, expected enrollment, study progress, baseline demographics, and observational phase data as well as tables presenting outcomes. It is the responsibility of the CSPCC Study Team to provide the DMC with whatever information the committee feels that it needs to successfully monitor the study. Thus, additional tables will be added as required by the DMC. In addition to the reports for the yearly meetings, the DMC will also be provided with reports between meetings at 6-month intervals.

The Data Monitoring Committee will receive reports from the analyses about three weeks prior to their annual meetings and at six-month intervals between meetings. These reports will include data on the participants enrolled, with an emphasis on a description of the participants at entry into the study, description of reasons for exclusion, dog behavior, and study and individual center performance with regards to participant intake and follow-up. Adverse event (AE) and serious adverse event (SAE) data will also be presented.

### 5.5.1.1 *Stopping Rules*

The DMC determined at their initial meeting that they would not utilize an interim analysis of the primary outcome to determine stopping rules. Instead they will analyze the safety data from the study, including AEs and SAEs, to determine if the study should terminate. This will continue throughout the study.

### 5.5.2 Executive Committee

The Executive Committee is the management and decision-making body for the operational aspects of the study and will monitor the performance of participating medical centers and the quality of data collected. The Executive Committee will formulate publication plans and will oversee the publication and presentation of all data from the study. The Executive Committee is comprised of the Chairmen, PPCSP Biostatistician and Project Manager, LSIs and Subject Matter Experts.

The Executive Committee will be presented with data that will allow the group to assess the quality of the data being submitted and how well the sites, in general, are adhering to the protocol. These data will also be presented by site, so sites performing substantially below average can be identified and remedial action can be taken to improve performance. One piece of information that will be routinely provided is the number of forms that are missing according to the participant's assessment schedule.

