Multivariate regressions will be used to evaluate the effect of assignment to intended treatment and quarter after enrollment on employment and on overall work productivity. Generalized Linear Model (GLM) regressions will be used, with Box-Cox regression used to identify the appropriate link function. A modified Park test will be used to identify the appropriate distributional family. Standard errors will be corrected for the correlation of multiple observations from the same trial participant over time. Two sets of analyses will be run for productivity. The first set of analyses will focus on work productivity and assign a value of 0% productivity to any individual who is not employed. The second set of analyses will focus on overall productivity and will use % Productivity at Work as a data point if the respondent was formally employed and % Productivity for ADL as a data point if the respondent was not formally employed.

- **Missing Data**

For this study we will collect data by in-person interviews and home visits, therefore we expect minimal missing data. When missing data are encountered in the analyses, a detailed sensitivity analysis can be conducted of the effects of various assumptions about the missing data. When needed, missing data will be imputed using standard multiple imputation techniques.

- **Interim Monitoring**

An independent oversight committee, a Data Monitoring Committee (DMC) will be monitoring study progress at predetermined time points over the entire duration of the study. The committee will receive analyses of the primary and the secondary outcome measures on a routine basis. Additionally, the committee will receive data on the participants enrolled, description of the reasons for participant exclusion, adverse events and each centers performance with regard to participant intake and follow-up. In general, this committee meets at six to nine months after the start of participant recruitment and at least annually (sometimes semiannually) thereafter. The committee will receive reports about three weeks prior to the meetings. Since the primary outcome measures are at 18 months, sufficient data for DMC's first review will not be available until the study has been ongoing for at least two years.

- **Criteria for Study Termination**

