The Data Monitoring Committee (DMC) will review the progress of the study and will monitor participant intake, outcomes, adverse events, and other issues related to participant safety. The DMC makes recommendations to the Director of the Clinical Science Research and Development (CSRD) Service about whether the study should continue or be stopped. The DMC will consist of experts in the fields of PTSD, Service Dogs, clinical trials, biostatistics, and ethics. These experts will not be participants in the trial and will not have participated in the planning of the protocol. The DMC will consider safety or other circumstances as grounds for early termination, including either compelling internal or external evidence of treatment differences or the unfeasibility of addressing the study hypothesis (e.g., poor participant intake, poor adherence to the protocol).

At each of its meetings during the study period, the DMC will review the randomization rates and assess the difference between the actual and the projected rates, as well as the impact of these assessments on overall trial size. If the study enrollment is inadequate, the reasons for exclusion may be scrutinized and actions may be suggested. An assessment of whether the trial should be continued will be made followed by recommendations, as appropriate. All serious adverse events will be reported on a regular basis to the DMC for their review. Unexpected serious adverse events will be reported to the DMC as soon as they become known based upon the consensus of the Study Chair, the Study Biostatistician, the Director, Perry Point CSPCC, and the Study Pharmacist. The Study Biostatistician will provide the appropriate data to the DMC at specified intervals for this purpose. Conditional power estimates will be provided to the DMC to assist them in making their decisions and recommendations.

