## **2.3 Derived variables**

### **2.3.1 WHODAS 2.0 Summary and Domain Scores**

The World Health Organization Disability Assessment Scale II (WHO-DAS 2.0) is a structured 36-item instrument, which assesses difficulties in six domains of life during the last 30 days. A total disability score is produced as well as domain scores. The domains include:

1. Cognition- understanding and communicating with the world
2. Mobility- moving and getting around
3. Self-care- attending to one's hygiene, dressing, eating and staying alone
4. Interpersonal interactions- getting along with people
5. Life activities- domestic responsibilities, leisure, and work
6. Participation in society-joining in community activities

The summary score is calculated using the 36 questions on the instrument. Summary scores can range from 0 to 100. Initially if any of the domain scores are missing, then the WHODAS summary score will be considered missing. However, if significant missing data is found, a sensitivity analyses will be computed, and the executive committee will determine if data should be imputed using standard multiple imputation methods.

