### 3.8 Sample Size

The goal for this study is a sample size of 220 including adjustment for subjects who withdraw or are lost-to-follow-up and interim analyses. In order to detect a 15% difference in mean scores for MCS (outcome requiring largest sample) over the 18-months of follow-up, at a statistical significance level of 0.05 (two-tailed test) and a power of 0.85, 82 participants per group will be needed, and 110 participants per treatment (220 total) will be required to account for a maximum of 25% post-pairing participant loss or dropout rate (see protocol). This sample size results in an expectation of 110 subjects in each of the treatment groups. For challenges in the recruitment of participants or in the pairing (or availability) of dogs, sample size will be revisited and adjusted accordingly taking into account the study's post-pairing termination rate. For 80%, a sample size of 72 per group is needed, and 90 participants per treatment (180 total) to account for a 20% post-pairing termination rate or 85 (170) to account for a 15% termination rate. When such challenges occur, a sample size of 180 will be the aim.

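### SAP 5.5 keeps comparative results from the Executive Committee, but SAP 5.5.2 seats on it the biostatistician role that supplies the DMC, with no recusal described, and that committee also decides whether the primary WHO-DAS total is imputed

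*SAP*

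**What the plan says.** **The bar.** SAP 5.5 states that the Study Chairmen, the Executive Committee and the scientific evaluation committee "will not be privy to any of the results that compare the outcomes of the two treatment groups".

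**The membership.** SAP 5.5.2: "The Executive Committee is comprised of the Chairmen, PPCSP Biostatistician and Project Manager, LSIs and Subject Matter Experts".

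**Who feeds the DMC.** Protocol XIX (Monitoring bodies): "The Study Biostatistician will provide the appropriate data to the DMC at specified intervals for this purpose". Protocol XIX (Study Management) puts the study biostatistician at the head of the coordinating-center (CSPCC) team. SAP 5.5.1 has that team report to the DMC, and the contents include "observational phase data as well as tables presenting outcomes". Protocol XVIII (Interim Monitoring) adds: "The committee will receive analyses of the primary and the secondary outcome measures on a routine basis".

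**What the committee decides.** In SAP 2.3.1, if missing data on the WHO-DAS summary score are significant, a sensitivity analysis is computed and "the executive committee will determine if data should be imputed using standard multiple imputation methods". SAP 2.3.5 repeats the rule for the PHQ-9. Under Protocol XIX (Monitoring participant intake) the committee may also add or drop centers or make minor changes to eligibility.

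**Sample size.** SAP 3.8 allows a lower target if recruitment or dog supply proves difficult: "When such challenges occur, a sample size of 180 will be the aim". It names no decision-maker.

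**The concern.** A rule that a committee does not see arm comparisons works only if nobody who produces those comparisons takes part in its decisions, or if that person steps out when it matters. Here a role on the producing side is also a listed member, and the plan does not say how the two are kept apart.

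Two things are at stake. First, the final report could not state without qualification that the Executive Committee worked without knowledge of comparative outcomes. That assurance carries weight here because, once the dog type is disclosed at the home clearing visit, the trial is open and its primary outcomes are self-reported. Second, the committee holds a discretionary decision on a primary outcome. What counts as significant missing data is undefined, and the decision comes after a sensitivity analysis has been computed. SAP 5.1 requires the SAP to be final only before the final analysis, so nothing fixes the imputation rule earlier.

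**Working it through.** **1. Is it the same role?** Protocol XIX (Study Management) lists the CSPCC team as the study biostatistician, a project manager, a statistical programmer, a database programmer and two computer assistants. There is no second statistician. SAP 5.5.2 seats the Perry Point biostatistician and project manager on the Executive Committee. The natural reading is that one biostatistician holds both positions. Two points leave some doubt: Protocol XIX (Monitoring data quality) uses the plural for biostatisticians, and the text just before the remaining staff roles in SAP 4.1 was not available for this check.

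**2. Do comparative outcomes exist during the trial?**

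| Points to yes | Points to no |
|---|---|
| Protocol XVIII, Interim Monitoring: routine primary and secondary outcome analyses for the DMC | Protocol XVIII, Criteria for Study Termination, and SAP 5.5.1.1: no interim analysis of the primary outcome for stopping |
| SAP 5.5.1: outcome tables in the report; large or small treatment differences are grounds for termination | SAP 5.5.1, closing paragraph: report contents listed without an outcome comparison |
| Protocol XIX: "Conditional power estimates will be provided to the DMC to assist them in making their decisions and recommendations" | That sentence names no preparer |

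The right-hand column withdraws a stopping rule. It does not withdraw the outcome reports. By-arm outcome results at interim are provided for but not fully reconciled.

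**3. Is there a safeguard?** The available text has no recusal rule, no unblinded statistician separate from the committee, and no limit on who prepares the DMC report. SAP 4.1 has the statistical programmer prepare reports for both committees while working closely with the biostatistician, so handing the tables to that person would separate little.

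**4. The size figures in SAP 3.8.** Inputs from Protocol Table 6 are MCS mean 33.2 and SD 10.6, so a 15% difference is 0.15 × 33.2 = 4.98. With n per group = 2(z₁ + z₂)²(SD/difference)²:

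- 85% power: 2 × (1.960 + 1.036)² × (10.6/4.98)² = 81.4, so 82; 82/0.75 = 109.3, so 110 per arm and 220 in total.
- 80% power: 2 × (1.960 + 0.842)² × (10.6/4.98)² = 71.1, so 72; 72/0.80 = 90 per arm and 180 in total; 72/0.85 = 84.7, so 85 per arm.

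All match the plan. The move to 180 lowers planned MCS power from 0.85 to 0.80 at 20% loss, and to about 0.78 if loss stays at 25% (90 × 0.75 = 67.5 evaluable per arm).

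**5. How much could a size choice informed by results matter?** Suppose, as an assumption, that someone sees the comparison at information equal to n₁ of the 180 and always picks whichever of 180 or 220 is more likely to give p < 0.05. Under no true difference, the final statistic at N, given an interim value z, is normal with mean z√(n₁/N) and variance 1 − n₁/N. Taking the larger of the two rejection probabilities and averaging over z gives the two-sided error of one test:

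| n₁ (assumed) | Error |
|---|---|
| 45 | 5.2% |
| 90 | 5.4% |
| 120 | 5.6% |
| 150 | 5.8% |

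This is a worst case for a decision that the documents do not give to this committee.

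**The case against.** The other side has real points.

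- SAP 5.5 is an express bar. It still covers the chairs, site investigators and subject matter experts, and nothing in either document sends comparative results to the committee. Its listed reports are operational. A reader might infer that there is no firewall at all; the documents do not support that. The gap is one seat.
- A reader might infer that the biostatistician prepares the conditional power estimates. Protocol XIX does not say who does, and because the DMC declined an interim efficacy analysis it is unclear whether they are still produced.
- A reader might infer that the Executive Committee can cut the sample on the strength of results. SAP 3.8 gives that decision to no one, its triggers are operational, and 180 is fixed in advance. Protocol XIX has the DMC consider the effect of randomization rates on trial size, and SAP 5.5.1 has it review all protocol changes.
- A reader might calculate that choosing between 180 and 220 raises the error to 7.0%. Two tests at |z| > 1.96 with correlation √(180/220) = 0.905 do give 0.0699, but only if the complete comparison on 180 is known when the size is chosen. Outcomes run to 18 months after pairing, and Protocol XVIII expects too little data for a first DMC review before about two years, so the enrollment decision would normally come first.
- The imputation rule is partly a separate matter. SAP 2.3.1 does not say that the committee sees by-arm results, and SAP 5.3 already makes the as-observed analysis primary. The missing threshold would be a weakness even with complete separation.

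These points limit the scope. They do not answer the conflict between SAP 5.5 and 5.5.2, or supply the missing safeguard.

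**Conclusion.** The point holds in a limited form. For one member of the Executive Committee, the plan's own membership list defeats the assurance in SAP 5.5, and no safeguard is described. That committee has an open-ended choice over imputation of one primary outcome (the WHO-DAS total) and one secondary outcome (the PHQ-9).

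No specific error rate follows from the documents. If results did influence the size choice, the illustration above puts the worst case for one test at about 5.2% to 5.8% instead of 5%, assuming information equal to 45 to 150 of the 180. The effect of a discretionary imputation choice cannot be quantified without knowing the amount and pattern of missing data.

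The conclusion rests on two assumptions: that the committee's biostatistician is the one who serves the DMC, which the staffing list strongly suggests, and that by-arm outcome tables reach the DMC before the trial ends, which the protocol and SAP provide for but do not fully reconcile. It should be put right because the correction is cheap and the assurance will be relied on when the trial is reported.

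**What to change.** 1. **SAP 5.5 and 5.5.2.** State that any biostatistician who has seen by-arm outcome results is recused from Executive Committee decisions on imputation, eligibility and sample size. Alternatively, have the closed DMC report prepared by coordinating-center staff who neither sit on that committee nor report to it. Moving the tables to the present statistical programmer is not enough.
2. **SAP 2.3.1 and 2.3.5.** Delete the committee's decision on imputation. Keep the as-observed analysis of SAP 5.3 as primary, and always run the multiply imputed version as a sensitivity analysis, whatever the amount of missing data.
3. **SAP 3.8.** State who decides a move to 180, and that the decision uses only recruitment, pairing and termination counts pooled over arms.

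The cost is wording in four SAP sections, a small reallocation of work inside the coordinating center and one extra analysis for each affected score. No change to data collection is needed.

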## 6 SUMMARY OF STUDY DATA

All continuous variables will be summarised using the following descriptive statistics: n (non-missing sample size), mean, standard deviation, median, maximum and minimum. The frequency and percentages (based on the non-missing sample size) of observed levels will be reported for all categorical measures. In general, all data will be listed, sorted by site, treatment (or screening) and subject. Summary tables with treatment should be structured with a column for each treatment group. For reporting data at study phases and visits, the order In Screening, Observation Phase, Clearing (waiting for pairing), and pairing visits should be used. Summary tables will be annotated with the total population size relevant to that table/treatment group.

### 6.1 Subject Disposition

Subject disposition will be summarized for all participants that signed the consent form, were randomized, and were paired. The following data will be presented:

- The number of participants enrolled and expected to be enrolled by site (TABLE 3).
- The number of participants screened and randomized by month for each site (TABLE 4).
- A cumulative summary of the participants in screening by site (TABLE 5).

- A listing of participants that discontinued from the study during screening. The listing will include the reasons for the exclusion of the participant from the study (TABLE 6).
- A figure of participants enrolled and expected by site (FIGURE 1).
- Subject disposition by site for all active participants (TABLE 7). The number of subjects that were randomized at each study center and the number and percentage of subjects that completed or discontinued after randomization at each study center will be summarized for each treatment group and for all participants.
  - The termination CRF will be used to determine randomized subjects who discontinued prematurely from the study.

## 6.2 Demographics

Subject demographics will be summarized for all study participants. Demographic characteristics of all study participants will include age, gender, ethnicity, income, and marital status. The summary will include:

- The number and percentage of participants with each category of gender, ethnicity, marital status, and income (TABLE 8).
- The sample size, mean, median, SD, minimum and Maximum values for the following:
  - Age
    - Age will be calculated using the date the participant was consented (year on Form 01) and the participant birth date (birth date on Form 01).

Estimates of the baseline demographic characteristics will be presented for all study participants. Tables summarizing the important background characteristics by site will be prepared and submitted to the Study Group to provide an idea of the population being studied and based on this information, comparisons of the participant characteristics among the sites will be possible.

## 6.3 Baseline Variables

### 6.3.1 WHO-DAS 2.0

The sample size, mean, median, SD, minimum, and maximum values for the WHO-DAS summary scores will be presented for the baseline visit.

